9.1.9 Warnings and Precautions

Hypertension: Serious complications of poorly controlled hypertension have been reported. Control blood pressure prior to initiating lenvatinib. Monitor blood pressure after 1 week, then every 2 weeks for the first 2 months, and then at least monthly thereafter during treatment. Withhold or discontinue for grade 3 hypertension despite optimal antihypertensive therapy. At treating physician's discretion, resume at a reduced dose when hypertension is controlled or permanently discontinue lenvatinib based on severity. Discontinue for grade 4 hypertension.

Cardiac Dysfunction: Serious and fatal cardiac dysfunction can occur with lenvatinib. Monitor patients for clinical symptoms or signs of cardiac dysfunction. Withhold or discontinue for grade 3 cardiac dysfunction. At treating physician's discretion, resume at a reduced dose upon recovery. Discontinue for grade 4 cardiac dysfunction.

Arterial Thromboembolic Events: Discontinue following an arterial thromboembolic event.

Hepatotoxicity: Monitor liver function prior to treatment and periodically (every 2 weeks for the first 2 months, and at least monthly thereafter) during treatment. Withhold or discontinue for grade 3 or 4 hepatotoxicity. Discontinue for hepatic failure.

Renal Failure or Impairment Serious including fatal renal failure or impairment can occur with lenvatinib. Initiate prompt management of diarrhea or dehydration/hypovolemia. Withhold and resume at a reduced dose upon recovery or permanently discontinue lenvatinib for renal failure or impairment based on severity.

Proteinuria: Monitor for proteinuria prior to treatment and periodically during treatment. Withhold for 2 or more grams of proteinuria per 24 hours. Discontinue for nephrotic syndrome.

Diarrhea: May be severe and recurrent. Promptly initiate management for severe diarrhea. Withhold and resume at a reduced dose upon recovery or permanently discontinue based on severity.

Fistula Formation and Gastrointestinal Perforation: Permanently discontinue in patients who develop grade 3 or 4 fistula or any grade gastrointestinal perforation.

QT Interval Prolongation: Monitor and correct electrolyte abnormalities. Withhold and resume at reduced dose of lenvatinib upon recovery based on severity for QT interval greater than 500 ms or for 60 ms or greater increase in baseline QT interval.

Hypocalcemia: Monitor blood calcium levels at least monthly and replace calcium as necessary. Withhold and resume at reduced dose upon recovery or permanently discontinue lenvatinib depending on severity.

Reversible Posterior Leukoencephalopathy Syndrome: Withhold and resume at a reduced dose upon recovery or permanently discontinue lenvatinib depending on severity and persistence of neurologic symptoms.

Hemorrhagic Events: Serious including fatal hemorrhagic events can occur with lenvatinib. Consider the risk of severe or fatal hemorrhage associated with tumor invasion or infiltration of major blood vessels (e.g., carotid artery). Withhold and resume at reduced dose upon recovery or permanently discontinue lenvatinib based on the severity.

Impairment of Thyroid Stimulating Hormone Suppression/Thyroid Dysfunction: Lenvatinib impairs exogenous thyroid suppression. Monitor thyroid function prior to initiating lenvatinib and at least monthly during treatment. Treat hypothyroidism according to standard medical practice.

Impaired Wound Healing: Impaired wound healing has been reported in patients who received lenvatinib. Withhold lenvatinib for at least 1 week prior to elective surgery. Do not administer for at least 2 weeks following major surgery and until adequate wound healing. The safety of resumption of lenvatinib after resolution of wound healing complications has not been established.

Osteonecrosis of the Jaw Osteonecrosis of the Jaw (ONJ): ONJ has been reported in patients receiving lenvatinib. Perform an oral examination prior to treatment with lenvatinib and periodically during lenvatinib treatment. Consider preventive dentistry prior to treatment with lenvatinib. Avoid invasive dental procedures, if possible, particularly in patients at higher risk. Withhold lenvatinib for at least 1 week prior to scheduled dental surgery or invasive dental procedures, if possible. Withhold lenvatinib if ONJ develops and restart based on clinical judgment of adequate resolution.

Embryofetal Toxicity: Lenvatinib can cause fetal harm. Advise of potential risk to a fetus and use of effective contraception during treatment and for at least 30 days after the last dose.

9.1.10 Adverse Events

See Section [9.2.11](#)

9.2 Pembrolizumab (Keytruda)

The following information is based on the Prescribing Information for Keytruda (pembrolizumab; MK-3475) dated July 2021.

9.2.1 Product Description

Pembrolizumab is a programmed death-receptor-1 (PD 1)-blocking antibody. Pembrolizumab is a humanized monoclonal IgG4 kappa antibody with an approximate molecular weight of 149 kDa. Pembrolizumab is produced in recombinant Chinese hamster ovary (CHO) cells.

KEYTRUDA (pembrolizumab) injection is a sterile, preservative-free, clear to slightly opalescent, colorless to slightly yellow solution for intravenous use. Each vial contains 100 mg of pembrolizumab in 4 mL of solution. Each 1 mL of solution contains 25 mg of pembrolizumab and is formulated in: L-histidine (1.55 mg), polysorbate 80 (0.2 mg), sucrose (70 mg), and Water for Injection, USP.

9.2.2 Mechanism of Action

Binding of the PD-1 ligands, PD-L1 and PD-L2, to the PD-1 receptor found on T cells, inhibits T-cell proliferation and cytokine production. Upregulation of PD-1 ligands occurs in some tumors and signaling through this pathway can contribute to inhibition of active T-cell immune surveillance of tumors. Pembrolizumab is a monoclonal antibody that binds to the PD-1 receptor and blocks its interaction with PD-L1 and PD-L2, releasing PD-1 pathway-mediated inhibition of the immune response, including the antitumor immune response. In syngeneic mouse tumor models, blocking PD-1 activity resulted in decreased tumor growth.

9.2.3 Storage and Handling Requirements

Store vials of solution under refrigeration at 2-8°C (36-46°F) in original carton to protect from light. Do not freeze. Do not shake.

9.2.4 Administration

Pembrolizumab is administered by intravenous infusion over 30 minutes through an intravenous line containing a sterile, non-pyrogenic, low-protein binding 0.2 micron to 5 micron in-line or add-on filter.

No other drugs should be co-administered through the same infusion line.

9.2.5 Preparation and Storage Following Dilution

Preparation for Intravenous Infusion

- Visually inspect the solution for particulate matter and discoloration. The solution is clear to slightly opalescent, colorless to slightly yellow. Discard the vial if visible particles are observed.
- Dilute pembrolizumab (solution) prior to intravenous administration.

- Withdraw the required volume from the vial(s) of pembrolizumab and transfer into an intravenous (IV) bag containing 0.9% Sodium Chloride Injection, USP or 5% Dextrose Injection, USP. Mix diluted solution by gentle inversion. Do not shake. The final concentration of the diluted solution should be between 1 mg/mL to 10 mg/mL.
- Discard any unused portion left in the vial.

Storage of Diluted Solution

The product does not contain a preservative. Store the diluted solution from the KEYTRUDA 100 mg/4 mL vial either:

- At room temperature for no more than 6 hours from the time of dilution. This includes room temperature storage of the diluted solution, and the duration of infusion.
- Under refrigeration at 2°C to 8°C (36°F to 46°F) for no more than 96 hours from the time of dilution. If refrigerated, allow the diluted solution to come to room temperature prior to administration. Do not shake.

Discard after 6 hours at room temperature or after 96 hours under refrigeration.

Do not freeze.

9.2.6 Availability and Ordering

Pembrolizumab is commercially available and administration is standard of care for patients with endometrial cancer. The costs of pembrolizumab and its administration will be the responsibility of the patient and/or the patient's 3rd party payor.

9.2.7 Contraindications

No contraindications have been identified.

9.2.8 Pharmacokinetics

The pharmacokinetics (PK) of pembrolizumab was characterized using a population PK analysis with concentration data collected from 2993 patients with various cancers who received pembrolizumab doses of 1 to 10 mg/kg every 2 weeks, 2 to 10 mg/kg every 3 weeks, or 200 mg every 3 weeks. Steady-state concentrations of pembrolizumab were reached by 16 weeks of repeated dosing with an every 3-week regimen and the systemic accumulation was 2.1-fold. The peak concentration (C_{max}), trough concentration (C_{min}), and area under the plasma concentration versus time curve at steady state (AUC_{ss}) of pembrolizumab increased dose proportionally in the dose range of 2 to 10 mg/kg every 3 weeks.

9.2.9 Drug Interactions

As pembrolizumab is an IgG4 antibody that is administered parentally and cleared by catabolism, food and drug-drug interactions are not anticipated to affect exposure. Therefore, no dedicated drug-drug interaction studies have been performed. However, as systemic corticosteroids may be used to treat immune-

mediated adverse reactions concomitant with pembrolizumab, the potential for a PK drug-drug interaction with pembrolizumab as a victim was assessed. No relationship was observed between prolonged use of systemic corticosteroids and pembrolizumab exposure. Similarly, the potential of drug-drug interaction between pembrolizumab and chemotherapy agents as well as other small molecules is expected to be low.

9.2.10 Warnings and Precautions

Severe and Fatal Immune-Mediated Adverse Reactions

Pembrolizumab is a monoclonal antibody that belongs to a class of drugs that bind to either the programmed death-receptor 1 (PD-1) or the PD-ligand 1 (PD-L1), blocking the PD-1/PD-L1 pathway, thereby removing inhibition of the immune response, potentially breaking peripheral tolerance and inducing immune-mediated adverse reactions. Important immune-mediated adverse reactions listed may not include all possible severe and fatal immune-mediated adverse reactions.

Immune-mediated adverse reactions, which may be severe or fatal, can occur in any organ system or tissue and can affect more than one body system simultaneously. Immune-mediated adverse reactions can occur at any time after starting treatment with a PD-1/PD-L1 blocking antibody. While immune-mediated adverse reactions usually manifest during treatment with PD-1/PD-L1 blocking antibodies, immune-mediated adverse reactions can also manifest after discontinuation of PD-1/PD-L1 blocking antibodies. Early identification and management of immune-mediated adverse reactions are essential to ensure safe use of PD-1/PD-L1 blocking antibodies. Monitor patients closely for symptoms and signs that may be clinical manifestations of underlying immune-mediated adverse reactions. Evaluate liver enzymes, creatinine, and thyroid function at baseline and periodically during treatment. In cases of suspected immune-mediated adverse reactions, initiate appropriate workup to exclude alternative etiologies, including infection. Institute medical management promptly, including specialty consultation as appropriate.

Withhold or permanently discontinue pembrolizumab depending on severity. In general, if pembrolizumab requires interruption or discontinuation, administer systemic corticosteroid therapy (1 to 2 mg/kg/day prednisone or equivalent) until improvement to grade 1 or less. Upon improvement to grade 1 or less, initiate corticosteroid taper and continue to taper over at least 1 month. Consider administration of other systemic immunosuppressants in patients whose immune-mediated adverse reactions are not controlled with corticosteroid therapy.

- Immune-mediated adverse reactions, including severe and fatal cases, have occurred in patients receiving pembrolizumab. Immune-mediated adverse reactions can occur after discontinuation of treatment. In clinical trials, most immune-mediated adverse reactions were reversible and managed with interruptions in pembrolizumab, administration of corticosteroids and/or supportive care. For additional information, refer to the current version of the Prescribing Information for pembrolizumab.
 - Immune-mediated pneumonitis

- Immune-mediated colitis
- Immune-mediated hepatitis
- Immune-mediated hypophysitis
- Adrenal insufficiency
- Immune-mediated hyperthyroidism and hypothyroidism
- Renal failure and immune-mediated nephritis
- Immune-mediated Type 1 diabetes mellitus
- The following additional clinically significant, immune-mediated adverse reactions occurred: severe skin reactions (including exfoliative dermatitis, Stevens-Johnson Syndrome, toxic epidermal necrolysis), uveitis, arthritis, myositis, pancreatitis, hemolytic anemia, partial seizures arising in a patient with inflammatory foci in brain parenchyma, adrenal insufficiency, myasthenic syndrome, optic neuritis, rhabdomyolysis, myocarditis, and myelitis
- Other immune-mediated adverse reactions:

The following clinically significant immune-mediated adverse reactions occurred at an incidence of <1% (unless otherwise noted) in patients who received pembrolizumab or were reported with the use of other PD 1/PD-L1 blocking antibodies. Severe or fatal cases have been reported for some of these adverse reactions.

 - *Cardiac/Vascular*: Myocarditis, pericarditis, vasculitis .
 - *Nervous System*: Meningitis, encephalitis, myelitis and demyelination, myasthenic syndrome/myasthenia gravis (including exacerbation), Guillain-Barré syndrome, nerve paresis, autoimmune neuropathy.
 - *Ocular*: Uveitis, iritis and other ocular inflammatory toxicities can occur. Some cases can be associated with retinal detachment. Various grades of visual impairment, including blindness, can occur. If uveitis occurs in combination with other immune-mediated adverse reactions, consider a Vogt-Koyanagi-Harada-like syndrome, as this may require treatment with systemic steroids to reduce the risk of permanent vision loss.
 - *Gastrointestinal*: Pancreatitis, to include increases in serum amylase and lipase levels, gastritis, duodenitis.
 - *Musculoskeletal and Connective Tissue*: Myositis/polymyositis, rhabdomyolysis (and associated sequelae, including renal failure), arthritis (1.5%), polymyalgia rheumatica.
 - *Endocrine*: Hypoparathyroidism Hematologic/Immune: Hemolytic anemia, aplastic anemia, hemophagocytic lymphohistiocytosis, systemic inflammatory response syndrome, histiocytic necrotizing lymphadenitis (Kikuchi lymphadenitis), sarcoidosis, immune thrombocytopenic purpura, solid organ transplant rejection.

- Transplant-related adverse reactions
 - Solid organ transplant rejection
 - Acute graft versus host disease (GVHD), including fatal GVHD, in patients with history of allogeneic hematopoietic stem cell transplant
- Increased mortality in patients with multiple myeloma when pembrolizumab is added to a thalidomide analogue and dexamethasone
- Infusion-related reactions, including hypersensitivity and anaphylaxis
- Embryofetal toxicity:

Pembrolizumab may cause fetal harm when administered to a pregnant woman. Highly effective contraception must be used during treatment with pembrolizumab and for 4 months after the last dose.

9.2.11 Adverse Events

The safety of pembrolizumab in combination with lenvatinib (20 mg orally once daily) was investigated in KEYNOTE-146, a single-arm, multicenter, open-label trial in 94 patients with endometrial carcinoma whose tumors had progressed following one line of systemic therapy and were not MSI-H or dMMR. The median duration of study treatment was 7 months (range: 0.03 to 37.8 months). The median duration of exposure to pembrolizumab was 6 months (range: 0.03 to 23.8 months).

Pembrolizumab was continued for a maximum of 24 months; however, treatment with lenvatinib could be continued beyond 24 months. Fatal adverse reactions occurred in 3% of patients receiving pembrolizumab and lenvatinib, including gastrointestinal perforation, reversible posterior leukoencephalopathy syndrome (RPLS) with intraventricular hemorrhage, and intracranial hemorrhage. Serious adverse reactions occurred in 52% of patients receiving pembrolizumab and lenvatinib.

Serious adverse reactions in $\geq 3\%$ of patients were hypertension (9%), abdominal pain (6%), musculoskeletal pain (5%), hemorrhage (4%), fatigue (4%), nausea (4%), confusional state (4%), pleural effusion (4%), adrenal insufficiency (3%), colitis (3%), dyspnea (3%), and pyrexia (3%). Pembrolizumab was discontinued for adverse reactions (grade 1-4) in 19% of patients, regardless of action taken with lenvatinib.

The most common adverse reactions ($\geq 2\%$) leading to discontinuation of pembrolizumab were adrenal insufficiency (2%), colitis (2%), pancreatitis (2%), and muscular weakness (2%).

Adverse reactions leading to interruption of pembrolizumab occurred in 49% of patients; the most common adverse reactions leading to interruption of pembrolizumab ($\geq 2\%$) were: fatigue (14%), diarrhea (6%), decreased appetite (6%), rash (5%), renal impairment (4%), vomiting (4%), increased lipase (4%), weight loss (4%), nausea (3%), increased blood alkaline phosphatase (3%), skin ulcer (3%), adrenal insufficiency (2%), increased amylase (2%), hypocalcemia (2%), hypomagnesemia (2%), hyponatremia (2%), peripheral edema (2%), musculoskeletal pain (2%), pancreatitis (2%), and syncope (2%). [Table 7](#) and

Table 8 summarize adverse reactions and laboratory abnormalities, respectively, in patients on pembrolizumab in combination with lenvatinib.

Table 7. Adverse Reactions Occurring in $\geq 20\%$ of Patients with Endometrial Carcinoma in KEYNOTE-146

Adverse Reaction	Pembrolizumab 200 mg every 3 weeks with Lenvatinib (n=94)	
	All Grades (%)	Grades 3-4 (%)
General		
Fatigue*	65	17
Musculoskeletal and Connective tissue		
Musculoskeletal pain†	65	3
Vascular		
Hypertension‡	65	38
Hemorrhagic events§	28	4
Gastrointestinal		
Diarrhea¶	64	4
Nausea	48	5
Stomatitis#	43	0
Vomiting	39	0
Abdominal pain¤	33	6
Constipation	32	0
Metabolism		
Decreased appetite¤	52	0
Anemia	27	3
Endocrine		
Hypothyroidism¤	51	1
Investigations		
Decreased weight	36	3
Nervous System		
Headache	33	1
Infections		
Urinary tract infection¤	31	4
Respiratory, Thoracic, and Mediastinal		
Dysphonia	29	0
Dyspnea¤	24	2
Cough	21	0
Skin and Subcutaneous Tissue		
Palmar-plantar erythrodysesthesia syndrome	26	3
Rash¤	21	3

* Includes asthenia, fatigue, and malaise

† Includes arthralgia, arthritis, back pain, breast pain, musculoskeletal chest pain, musculoskeletal pain, musculoskeletal stiffness, myalgia, neck pain, non-cardiac chest pain, pain in extremity

‡ Includes essential hypertension, hypertension, and hypertensive encephalopathy

§ Includes catheter site bruise, contusion, epistaxis, gastrointestinal hemorrhage, hematemesis, hematuria, hemorrhage intracranial, injection site hemorrhage, intraventricular hemorrhage, large intestinal hemorrhage, metrorrhagia, mouth hemorrhage, uterine hemorrhage, and vaginal hemorrhage

¶ Includes diarrhea, gastroenteritis, gastrointestinal viral infection, and viral diarrhea

Includes glossitis, mouth ulceration, oral discomfort, oral mucosal blistering, oropharyngeal pain, and stomatitis

¤ Includes abdominal discomfort, abdominal pain, lower abdominal pain, and upper abdominal pain

¤ Includes decreased appetite and early satiety

¤ Includes increased blood thyroid stimulating hormone and hypothyroidism

¤ Includes cystitis and urinary tract infection

δ Includes dyspnea and exertional dyspnea
 ø Includes rash, rash generalized, rash macular, and rash maculo-papular

Table 8. Laboratory Abnormalities Worsened from Baseline Occurring in ≥20% (All Grades) or ≥3% (Grades 3-4) of Patients with Endometrial Carcinoma in KEYNOTE-146

Laboratory Test*	Pembrolizumab 200 mg every 3 weeks with Lenvatinib (n=94)	
	All Grades (%)†	Grades 3-4 (%)†
Chemistry		
Increased creatinine	80	7
Hypertriglyceridemia	58	4
Hyperglycemia	53	1
Hypercholesterolemia	49	6
Hypoalbuminemia	48	0
Hypomagnesemia	47	2
Increased aspartate aminotransferase	43	4
Hyponatremia	42	13
Increased lipase	42	18
Increased alanine aminotransferase	35	3
Increased alanine phosphatase	32	1
Hypokalemia	27	5
Increased amylase	19	6
Hypocalcemia	14	3
Hypermagnesemia	4	3
Hematology		
Thrombocytopenia	48	0
Leukopenia	38	2
Lymphopenia	36	7
Anemia	35	1
Increased INR	21	3
Neutropenia	12	3

* With at least 1 grade increase from baseline

† Laboratory abnormality percentage is based on the number of patients who had both baseline and at least one post-baseline laboratory measurement for each parameter (range: 71 to 92 patients).

10 MEASUREMENT OF EFFECT

10.1 Evaluation Criteria for Tumor Response

Tumor response will be evaluated and recorded according to RECIST v1.1.

In the event of a PR or CR, the imaging used when the response was first documented must be repeated at the time of the next scheduled imaging to confirm tumor response. At the treating physician's discretion, confirmatory scans can be performed sooner, but no less than 4 weeks following the imaging indicating the PR or CR.

10.2 Imaging

Only imaging of the initial sites of disease is required at subsequent time points to provide tumor measurements for assessment of antitumor effect. History of brain metastases should prompt brain imaging at baseline and periodically after initiation of study therapy.

The same type of imaging used at baseline should be used at each scheduled assessment. At the treating physician's discretion, additional imaging may be performed when clinically indicated.

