2.2 Secondary Objectives

- 2.2.1 Determine median PFS in the study population
- 2.2.2 Determine the incidence of treatment-related AEs in the study population
- 2.2.3 Determine the number of patients who discontinue treatment due to treatment-related AEs

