- K. Brain imaging only required for patients with brain metastasis diagnosed and treated prior to initiation of study treatment. The imaging used at baseline should be used at each subsequent imaging time point.
- L. Counting from C1D1, for the first 24 weeks, during Week 6, 12, 18, and 24 (±1 week), or sooner, if clinically indicated, until documentation of confirmed progression. After 24 weeks, tumor assessments must be performed every 9 weeks counting from C1D1 (during Week 33, 42, 51, 60, etc.) (±1 week), or sooner if clinically indicated, until documentation of confirmed PD. Responses and PD must be confirmed at least 4 weeks later (usually at the next tumor assessment).
- M. PROs will be administered every day 1 of every cycle starting at C1D1 and 30 days after last dose of study drug until patient enters the extended follow-up period. During the extended follow-up period PROs will be administered every 3 months (see Section [1.4.1](#)).
- N. FACIT/HADS questionnaire will be administered at baseline, C1D1, C2D1, C3D1, then every other cycle beginning at C5 and beyond, end of study, and the first extended follow-up visit (see Section [1.4.1](#)).
- O. Collect correlative whole blood urine, and vaginal swab samples any time after consent and before C1D1 prior to the initiation of any study treatment. See also Section [11](#).
- P. An optional additional blood sample will be collected for DNA ancestral analysis. See [Section 11.3.1](#)
- Q. Collect correlative whole blood at the conclusion of therapy if prior to 90 days. See also Section 11
- R. Capture survival status approximately every 3 months during the extended follow-up period. During the extended follow-up period, data may be obtained by record review or patients may be contacted by phone for report of disease status, new treatment and/or survival status approximately every 3 months.
- S. Lenvatinib administered orally (PO) once daily (QD) during each 21-day cycle For lenvatinib instructions refer to Sections [6.2](#), [7.3](#), and [9.1](#).
- T. Pembrolizumab administered by IV infusion on day 1 of each 21-day cycle. For pembrolizumab instructions refer to Sections [6.2](#), [7.4](#), and [9.2](#).

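### Section 10.2 requires follow-up imaging only of the initial disease sites, so a silent new lesion can be missed, which can bias median PFS and, less so, 24-week ORR upward

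*Combined protocol and SAP*

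**What the plan says.** On coverage, Section 10.2 (Imaging) reads: "Only imaging of the initial sites of disease is required at subsequent time points to provide tumor measurements for assessment of antitumor effect". On method it adds: "The same type of imaging used at baseline should be used at each scheduled assessment". Anything beyond that is optional: "At the treating physician's discretion, additional imaging may be performed when clinically indicated".

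Section 12, footnote K, says "Brain imaging only required for patients with brain metastasis diagnosed and treated prior to initiation of study treatment" and then "The imaging used at baseline should be used at each subsequent imaging time point". Footnote L sets the first scans "during Week 6, 12, 18, and 24 (±1 week), or sooner, if clinically indicated", then every 9 weeks from week 33.

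The endpoints that depend on these scans are response, for which Section 10.1 says "Tumor response will be evaluated and recorded according to RECIST v1.1", and the first secondary objective in Section 2.2, "Determine median PFS in the study population". Section 13.1 measures PFS from treatment start to progression or censoring. Section 10.3 provides for central review of the transmitted images once a patient is off treatment. Under Section 6.5.2, patients who stop treatment without progression are followed for PFS by reported clinical status every 3 months.

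The documents nowhere define which body regions the baseline scan covers, and they do not ask for a search for new lesions at scheduled assessments.

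**The concern.** Measuring known lesions is enough to record shrinkage. It is not enough to rule out progression, because under the adopted criteria a new lesion also counts as progression. (The protocol cites RECIST v1.1 and does not reproduce it.)

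Take, as an illustration, a patient whose baseline disease is confined to the pelvis. A site that follows Section 10.2 literally may scan only the pelvis from week 6 on. A silent lesion in another organ then lies outside every required scan. The patient stays on record as stable or responding until an examination, a laboratory result or a clinically indicated scan reveals it.

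A missed new lesion can only hide progression or delay its date. It cannot create a progression, so PFS and ORR stay the same or rise. The trial is single-arm (Section 3.1), so no concurrent control shares the error, and its results will naturally be read beside the 36.2% ORR cited in Section 1.3. Coverage may also differ among the up to 10 sites, since the text allows both minimal and full repeat scans.

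**Working it through.** **1. Does another provision close the gap?**

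- The sentence in 10.2 on type of imaging fixes the method, not the body regions.
- Footnote K comes closest. It names no body region, uses 'should', and follows a sentence about brain metastases. If full repetition was intended, it conflicts with 10.2.
- Section 10.1 has the response-documenting imaging repeated for confirmation. A narrow first scan is then confirmed by another narrow scan.
- Central review sees only images that were taken.
- Extra imaging is discretionary and triggered by clinical findings.

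None of these requires coverage beyond the initial sites.

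**2. The plan's own figure.** Section 13.2 gives a margin of ±0.1 for 100 patients at ORR 0.5. The Wald half-width is 1.96 × √(0.5 × 0.5 / 100) = 0.098, and the Wilson half-width for 50/100 is 0.096. The figure reproduces. It covers sampling error only, so the fix leaves it unchanged.

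**3. PFS (all inputs assumed).** Let m be the true median (5, 7 or 9 months), q the share of progressions that occur first and only at a new site, and L the median of an exponential extra detection lag (2 or 4 months). With λ = ln 2 / m and μ = ln 2 / L, the recorded progression-free curve is

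S(t) = (1 − q)·e^(−λt) + q·[μ·e^(−λt) − λ·e^(−μt)] / (μ − λ).

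The recorded median solves S(t) = 0.5. Check for m = 7, L = 4, q = 0.20: λ = 0.0990 and μ = 0.1733. At t = 8.15, e^(−λt) = 0.446 and e^(−μt) = 0.244, so the bracketed term divided by (μ − λ) is 0.716. Then S = 0.8 × 0.446 + 0.2 × 0.716 = 0.500.

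Shift in the underlying median, in months (L = 2 to L = 4):

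| q | m = 5 | m = 7 | m = 9 |
|---|---|---|---|
| 5% | 0.16-0.24 | 0.17-0.28 | 0.17-0.30 |
| 10% | 0.31-0.48 | 0.33-0.56 | 0.34-0.61 |
| 20% | 0.64-1.01 | 0.66-1.15 | 0.67-1.24 |

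**4. The same curves on the scan schedule.** The observed median is the first scheduled scan at which S is at or below 0.5. With full detection this is week 24, 33 or 42 for m = 5, 7 or 9.

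- At q = 5% or 10% it does not move in any of these cases, although at 10% with L = 4 the curve is only just under 0.5 (0.498 to 0.499).
- At q = 20% it moves one scan later in five of the six cases. The sixth (m = 9, L = 2) sits on the threshold at week 42.
- For m = 7, S at week 33 goes from 0.472 with full detection to 0.504-0.526 at q = 20%. A change of 0.03 to 0.05 crosses 0.5 and so appears as a 9-week jump.

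**5. ORR.** With 100 patients, each responder with an unseen new lesion adds 1/100, or 1 percentage point. If a share s of recorded responders is affected, the overstatement is recorded ORR × s. For s = 5% and 10% (assumed), that is 0.018 and 0.036 at a recorded 0.362, and 0.025 and 0.050 at 0.50. As an illustration of what such a bias does, summing binomial probabilities over the counts whose Wilson interval contains a true ORR of 0.362 gives 95.2% coverage with no bias and 92.5% with an upward bias of 0.02.

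**The case against.** The best counter-argument is that a site may fairly read footnote K, together with the confirmation rule in 10.1, as repeating the whole baseline scan. Sites that do so would have little or no bias. The narrow-scan scenario also assumes that the baseline scan was wider than the follow-up scans, and the documents specify neither. This stands as far as it goes: the defect is wording that permits narrow coverage, and narrow coverage has not been shown to occur.

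There are real partial safeguards. History, physical examination and chemistry with a hepatic panel recur every cycle, and scans can be added or brought forward when clinically indicated. They reduce the exposure to asymptomatic lesions outside the imaged regions, but do not remove it.

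Two stronger inferences are tempting. One is that ORR, as the primary endpoint, is the main casualty. ORR changes only if target lesions shrink to a response while an unseen new lesion is already present. If the endpoint means best confirmed response by week 24, the lesion must also precede confirmation. The protocol does not say which definition applies, so ORR is the less exposed of the two endpoints. The other inference is that median PFS would be overstated by about 2 months, the distance from week 33 to week 42. That is a step effect of the scan schedule, and the underlying shift in that example is 0.66 to 1.15 months.

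**Conclusion.** The gap in the text is real and worth closing. Section 10.2 limits required follow-up imaging to the initial disease sites, and no other provision clearly overrides it. Following the text can delay or hide progression at a new site, so it can bias median PFS upward and, to a lesser degree, 24-week ORR.

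A reader might conclude that both endpoints are biased. The documents do not support that: they give neither the frequency of new-site-only progression, nor the detection delay, nor actual scanning practice. The size is conditional on the assumptions in the working: about 0.2-0.3, 0.3-0.6 and 0.6-1.2 months on the underlying median for q of 5%, 10% and 20%. On the scan schedule, the observed median does not move at 5% or 10% and usually moves one scan at 20%. Confidence is high about the wording and low about the size of the effect.

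**What to change.** Replace the coverage sentence in Section 10.2 with: *Every scheduled tumor assessment repeats the full anatomical coverage of the baseline scan by the same method, and all images are read for new lesions as well as target and non-target lesions.* Align footnote K with it and keep the brain-imaging requirement as stated.

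This adds no visits or readers. The cost is a wider field on scans already scheduled for some patients with limited disease, with some added radiation and expense. Which regions the baseline scan must cover is a separate design choice for the sponsor, and closing this gap does not depend on it.
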